### **6.2.2. *Prior/Concomitant Therapy***

- [29] have used or intend to use over-the-counter or prescription medication (herbal supplements, systemic glucocorticoids, immunomodulatory drugs, drugs with propensity for dermal reactions, drugs with known liver toxicity, etc.) within 7 days prior to dosing and during the study without agreement by the sponsor; for inclusion, stable doses of antihypertensive agents, aspirin, and lipid-lowering agents are allowed; occasional paracetamol/acetaminophen up to a 2-g dose in a 24-hour period may be allowed for inclusion at the discretion of the investigator (refer to Section 7.7)
- [30] have a history of insulin therapy except for the use of insulin for treatment of gestational diabetes or acute, temporary use of insulin ( $\leq 14$  days), for example, for acute illness, hospitalization, elective surgery
- [31] have received chronic (lasting  $>14$  consecutive days) systemic glucocorticoid therapy (excluding topical, intra-articular, and inhaled preparations) in the past year or have received any glucocorticoid therapy within 30 days before screening
- [32] have used any traditional Chinese treatments within 30 days prior to study enrollment or intend to use any traditional Chinese treatment during the study

### **6.2.3. *Prior/Concurrent Clinical Trial Experience***

- [33] are currently enrolled in a clinical study involving an IP or any other type of medical research judged not to be scientifically or medically compatible with this study
- [34] have participated, within the past 30 days, in a clinical study involving an IP. If the previous IP has a long half-life, 5 half-lives or 30 days (whichever is longer) should have passed
- [35] have previously completed or withdrawn from this study or any other study investigating tirzepatide, and have previously received the IP

### **6.2.4. *Other Exclusions***

- [36] are study site or hospital personnel directly affiliated with this study and their immediate families. Immediate family is defined as a spouse, biological or legal guardian, child, or sibling.
- [37] are Lilly employees
- [38] are women who are lactating

- [39] have donated blood of more than 400 mL within the previous 12 weeks (males) or in the past 16 weeks (females), any blood donation (including apheresis) within the past 4 weeks, or total volume of blood donation in the past year is 1200 mL (males) or 800 mL (females) or more at screening
- [40] have an average weekly alcohol intake that exceeds 21 units per week (males) and 14 units per week (females) (1 unit = 12 oz or 360 mL of beer, 5 oz or 150 mL of wine, 1.5 oz or 45 mL of distilled spirits) or are unwilling to stop alcohol consumption during the 24 hours before and 72 hours post dose administration, and 24 hours before each admission to CRU and each outpatient visit, and throughout the duration of each CRU visit
- [41] currently smoke in excess of 10 cigarettes/day or use tobacco or nicotine substitutes (within the past 6 months of screening), or subjects unwilling to refrain from smoking or are unable to abide by CRU restrictions
- [42] regularly use known drugs of abuse or show positive findings on drug screening
- [43] in the opinion of the investigator or sponsor, are unsuitable for inclusion in the study

### **6.3. Lifestyle and/or Dietary Requirements**

Throughout the study, patients may undergo medical assessments and review of compliance with requirements before continuing in the study.

#### ***6.3.1. Meals and Dietary Restrictions***

Patients will be required to fast overnight for at least 8 hours on fasting visit as described in the Schedule of Activities (Section 2). During fasting, water may be consumed freely. Standard meals will be provided after approximately 15 minutes from IP administration in the CRU. Standardized lunch and dinner meals will be provided in the CRU to assess meal intake and subjective rating of appetite sensation (Section 9.6.2).

When not residing in the CRU, patients should maintain their routine prestudy dietary patterns as much as possible.

### ***6.3.2. Caffeine, Alcohol, and Tobacco***

**Caffeine:** During the stay at CRU, patients should refrain from caffeinated foods and beverages such as cola, chocolate drinks, tea, and coffee. Patients will be allowed to maintain their regular caffeine consumption outside the CRU throughout the study period.

**Alcohol:** No alcohol will be allowed 24 hours before each admission to CRU and each outpatient visit, throughout the duration of each CRU visit, and 72 hours following IP administration. Between CRU visits, daily alcohol consumption should not exceed 3 units for males and 2 units for females (a unit is defined in Exclusion Criterion [40], Section [6.2](#))

**Tobacco:** No nicotine use will be permitted while at the CRU. When not at the CRU, patients may smoke no more than 10 cigarettes or consume the equivalent amount of nicotine per day.

### ***6.3.3. Activity***

Patients will be advised to maintain their regular levels of physical activity/exercise during the study. When certain study procedures are in progress at the site, patients may be required to remain supine, recumbent, or sitting.

## **6.4. Screen Failures**

Individuals who do not meet this study's participation criteria may be re-screened once. The interval between re-screenings should be at least 2 weeks. If re-screened, the individual must sign a new ICF and will be assigned a new identification number. Repeating laboratory or clinical tests is not considered a re-screen.

## 7. Treatment

### 7.1. Treatment Administered

This study involves a comparison of QW SC dose levels of tirzepatide (2.5 mg to 10 mg titration regimen for Cohort 1 and 2.5 mg to 15 mg titration regimen for Cohort 2) with corresponding volume-matched placebo. [Table GPHT.2](#) shows the treatment regimens.

For Cohort 1, the starting dose of tirzepatide will be 2.5 mg QW for 4 weeks, then the dose will be increased by 2.5 mg every 4 weeks (2.5 mg to 5 mg to 7.5 mg to 10 mg) until the 10-mg dose is reached and maintained for the duration of the study. For Cohort 2, the starting dose of tirzepatide will be 2.5 mg QW for 4 weeks, then the dose will be increased by 2.5 mg every 4 weeks (2.5 mg to 5 mg to 7.5 mg to 10 mg to 12.5 mg to 15 mg) until the 15-mg dose is reached and maintained for the duration of the study.

**Table GPHT.2. Tirzepatide Treatment Regimens**

Cohort	Treatment Period Interval					
	Weeks	Weeks	Weeks	Weeks	Weeks	Weeks
	0 to 3	4 to 7	8 to 11	12 to 15	16 to 19	20 to 23
1	2.5 mg	5 mg	7.5 mg	10 mg		
2	2.5 mg	5 mg	7.5 mg	10 mg	12.5 mg	15 mg

Note: All doses will be administered once weekly using a single-dose pen.

All injections will be administered into the SC tissue of the abdominal wall. Injection sites will be alternated weekly between 4 sites on the abdominal wall (that is, right and left upper quadrants and right and left lower quadrants). During CRU visits as shown in the Schedule of Activities, Section 2, site staff will administer SC doses of tirzepatide or placebo. For dosing at non-CRU visits, patients may either self-administer or visit the CRU to have staff administer SC doses of tirzepatide or placebo.

The investigator or designee is responsible for

- explaining the correct use of the IP to the site personnel and the patient
- verifying that instructions are followed properly
- maintaining accurate records of IP dispensing and collection
- instructing patients to discard all used single-dose pens (SDPs) for tirzepatide in a closeable, puncture-resistant container and dispose according to local regulations

### ***7.1.1. Packaging and Labeling***

The sponsor will provide tirzepatide in SDP. These will be dispensed via an interactive web-response system (IWRS). SDP will be packaged in cartons to be dispensed. Each SDP contains a specific dose and is administered as a single injection. The SDP will be packaged for each dose strength: 2.5mg, 5mg, 7.5mg, 10mg, 12.5mg, 15mg and placebo to match. The IP will be labeled according to the country's regulatory requirements.

### ***7.1.2. Medical Devices***

The products provided for use in the study are tirzepatide investigational SDP.

## **7.2. Method of Treatment Assignment**

Patients who meet all criteria for enrollment will be randomized to receive either tirzepatide or placebo in a 5:1 ratio at Visit 3a. Assignment to treatment groups will be determined by a computer-generated random sequence using an IWRS.

### ***7.2.1. Selection and Timing of Doses***

There are no restrictions on the time of day each weekly dose of tirzepatide is given, but it is advisable to administer the SC injections on the same day and same time each week. The actual date and time of dose administrations will be recorded by investigator at dosing visit on site or by the patient on self-administration day.

If a dose of tirzepatide is missed, the patient should take it as soon as possible unless it is within 72 hours of the next dose, in which case, that dose should be skipped and the next dose should be taken at the appropriate time. Missed doses may not result in patient discontinuation from the study. For more information on missed doses, please refer to Section [7.6](#).

## **7.3. Blinding**

The dosing regimen is patient- and investigator-blind. Investigators, site staff, clinical monitors, and patients will remain blinded to the treatment assignments until the study is complete. Blinding will be maintained throughout the study as described in the separate Blinding Plan.

Emergency unblinding for AEs may be performed through the IWRS, which may supplement or take the place of emergency codes generated using a computer drug-labeling system. This option may be used ONLY if the patient's well-being requires knowledge of the patient's treatment assignment. All calls resulting in an unblinding event are recorded and reported by the IWRS.

If a patient's study treatment assignment is unblinded, the patient must discontinue from the study, unless the investigator obtains specific approval from a Lilly clinical pharmacologist or clinical research physician (CRP) for the study participant to continue in the study. During the study, emergency unblinding should occur only by accessing the study patient's emergency code.

In case of an emergency, the investigator has the sole responsibility for determining if unblinding of a patient's treatment assignment is warranted for medical management of the event. The patient's safety must always be the first consideration in making such a determination. If the investigator decides that unblinding is warranted, the investigator must promptly document the decision and rationale and notify Lilly as soon as possible.

For the blinded items in the clinical laboratory tests, please refer to [Appendix 2](#).

## 7.4. Dose Modification

Dose adjustments are not permitted in this study.

## 7.5. Preparation/Handling/Storage/Accountability

The investigator or designee must confirm the maintenance of appropriate temperature conditions (2°C to 8°C), as communicated by the sponsor, during transit for all IPs received. The investigator or designee should report and resolve any discrepancies before use of the IP.

Only participants enrolled in the study may receive the IPs or study materials, and only authorized site staff may supply or administer IP. All IPs should be stored in an environmentally controlled and monitored (manual or automated) area in accordance with the labeled storage conditions with access limited to the investigator and authorized site staff.

The investigator, institution, or the head of the medical institution (where applicable) is responsible for IP accountability, reconciliation, and record maintenance (such as receipt, reconciliation, and final disposition records).

Patients will receive insulated bags with cooling gel packs for use in transporting the IP carton from the site to home.

Study site staff must regularly assess whether the patient is correctly administering the assigned IP and storing the study drug according to the provided instructions.

## 7.6. Treatment Compliance

Study drug compliance will be determined by the following:

- study drug administration data will be recorded by the investigator or patient (self-administration), and reviewed by the investigator at each study visit and

- the patients will be instructed to return any unused study drug and/or empty cartons at the next visit to the study site for the purpose of performing drug accountability.

Patients who are significantly noncompliant will be permanently discontinued from study medication. A patient will be considered significantly noncompliant if he /she misses 4 or more doses of study medication. Similarly, a patient will be considered significantly noncompliant if they are judged by the investigator to have intentionally or repeatedly taken more than the prescribed amount of medication.

In addition to the assessment of a patient's compliance with IP administration, other aspects of compliance with the study treatments will be assessed at each visit based on the patient's adherence to the visit schedule, compliance with the concomitant medication, completion of study diaries, the results of home blood glucose monitoring, and any other parameters the investigator considers necessary.

Initially, patients considered to be poorly compliant with their medication and/or the study procedures will receive additional training and instruction, as required, and will be reminded of the importance of complying with the protocol.

## 7.7. Concomitant Therapy

Treatment with drugs that are excluded under the entry criteria (Section 6) is not permitted. These medications include traditional Chinese medicines, herbal supplements, systemic glucocorticoids, immunomodulatory drugs, drugs with propensity for dermal reactions, drugs with known liver toxicity, etc.

Patients on stable concomitant medication at the time of study entry should continue their regular, unchanged dose throughout the study. These medications (refer to Section 6) include antihypertensive agents, aspirin, and lipid-lowering agents.

Apart from those listed earlier, patients should avoid concomitant medication; however, at their discretion, the investigator may administer acetaminophen (1 g, maximum 2 g/day) for treatment of headache, etc. If the need for concomitant medication (other than acetaminophen) arises, inclusion or continuation of the patient may be at the discretion of the investigator after consultation with a Lilly clinical pharmacologist, CRP, or clinical research scientist (CRS).

Study site personnel will record any concomitant medications used during the course of the study in the electronic case report form (eCRF).

### ***7.7.1. Management of Patients with Gastrointestinal Symptoms***

Patients will be guided on dietary behaviors that may help mitigate symptoms of nausea and vomiting, for example, eating smaller meals, splitting 3 daily meals into 4 or smaller ones, and stopping eating when they feel full. For patients experiencing intolerable persistent GI symptoms, the investigator may consider prescribing symptomatic medication (for example, antiemetic medication).

### **7.8. Treatment after the End of the Study**

Not applicable for this study.

## 8. Discontinuation Criteria

Patients discontinuing from the treatment prematurely for any reason should complete AE and other follow-up procedures per Section 2 of this protocol.

### 8.1. Discontinuation from Study Treatment

Discontinuation of the IP for abnormal liver tests should be considered by the investigator when a patient meets 1 of the following conditions after consultation with the Lilly-designated medical monitor:

- ALT or AST  $>8X$  ULN
- ALT or AST  $>5X$  ULN sustained for more than 2 weeks or
- ALT or AST  $>3X$  ULN and TBL  $>2X$  ULN or international normalized ratio  $>1.5$  or
- ALT or AST  $>3X$  ULN with the appearance of fatigue, nausea, vomiting, right upper-quadrant pain or tenderness, fever, rash, and/or eosinophilia ( $>5\%$ )
- alkaline phosphatase (ALP)  $>3X$  ULN
- ALP  $>2.5X$  ULN and TBL  $>2X$  ULN
- ALP  $>2.5X$  ULN with the appearance of fatigue, nausea, vomiting, right quadrant pain or tenderness, fever, rash, and/or eosinophilia ( $>5\%$ ).

In addition, a patient will be discontinued from using the IP in case of abnormal pancreatic tests when he or she meets the following condition:

- lipase and/or amylase are confirmed to be  $\geq 3 \times$  ULN. Please refer to the algorithm for the monitoring of pancreatic events in [Appendix 5](#).

#### 8.1.1. Discontinuation of Inadvertently Enrolled Patients

If the sponsor or investigator identifies a patient who did not meet enrollment criteria and was inadvertently enrolled, a discussion must occur between the Lilly clinical pharmacologist/CRP and the investigator to determine if the patient may continue in the study. If both agree, it is medically appropriate to continue, the investigator must obtain documented approval from the Lilly clinical pharmacologist/CRP to allow the inadvertently enrolled patient to continue in the study with or without continued treatment with IP.

## 8.2. Discontinuation from the Study

Patients will be discontinued under the following circumstances:

- enrollment in any other clinical study involving an IP or enrollment in any other type of medical research judged not to be scientifically or medically compatible with this study
- participation in the study needs to be stopped for medical, safety, regulatory, or other reasons consistent with applicable laws, regulations, and good clinical practice (GCP)
- Investigator decision
  - the investigator decides that the patient should be discontinued from the study
  - if the patient, for any reason, requires treatment with another therapeutic agent that has been demonstrated to be effective for treatment of the study indication, discontinuation from the study occurs prior to introduction of the new agent
- Patient decision
  - the patient, or legal representative, requests to be withdrawn from the study.

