a A patient who discontinues from Cohort 1 between Day 1 and Day 113, inclusive, will complete ED1 procedures as soon as possible. The patient will be asked to complete ED2 procedures after a washout period of at least 28 days from the last IP administration. The patient who discontinues from Cohort 1 after the completion of Day 113 will complete ED2 procedures after a washout period of at least 28 days from the last IP administration. A patient who discontinues from Cohort 2 between Day 1 and Day 169, inclusive, will complete ED1 procedures as soon as possible. The patient will be asked to complete ED2 procedures after a washout period of at least 28 days from the last IP administration. The patient who discontinues from Cohort 2 after the completion of Day 169 will complete ED2 procedures after a washout period of at least 28 days from the last IP administration.

b Patients will be required to fast overnight for at least 8 hours before taking the first SC dose of tirzepatide (or placebo) and before each blood sample draw on fasting visit.

c Weight will be measured in a consistent way per Section 9.1, always predose.

d Full physical examination / medical assessment at screening. Symptom-directed physical examination/medical assessment at all other time points, and as deemed necessary by the investigator.

e Patients who have completed chest x-ray within the past 12 months and whose x-ray and/or report are available for review are exempt from the chest x-ray examination. The required chest x-ray is a single posterior anterior (PA) x-ray. If evidence of an abnormality, a lateral chest x-ray will be performed.

f These tests will be performed at the local laboratory.

g Additional urine drug screen or breath ethanol tests may be performed at the investigator's discretion.

h Females only. Blood pregnancy test will be done on screening; urine test at other times as indicated, or when performed at the investigator's discretion.

i Patients will conduct the 7-point SMPG every 3 days since Day -13 during lead-in period and will record readings in patient diary.

j A maximum of 3 samples may be collected at additional time points during the study if warranted and agreed upon by both the investigator and sponsor.

k Patients may be required to remain at the CRU longer than the planned discharge day at the investigator's discretion to assure patients' safety or to provide additional safety monitoring.

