#### 9.4.4.2. Pancreatic Safety

Acute pancreatitis is defined as an AE of interest in all trials with tirzepatide including this trial. Acute pancreatitis is an acute inflammatory process of the pancreas that may also involve peripancreatic tissues and/or remote organ systems (Banks and Freeman 2006). The diagnosis of acute pancreatitis requires 2 of the following 3 features:

- abdominal pain, characteristic of acute pancreatitis (generally located in the epigastrium and radiates to the back in approximately half the cases [Banks and Freeman 2006; Koizumi et al. 2006]; the pain is often associated with nausea and vomiting)
- serum amylase (total and/or pancreatic) and/or lipase  $\geq 3X$  ULN
- characteristic findings of acute pancreatitis on computed tomography (CT) scan or magnetic resonance imaging (MRI)

If acute pancreatitis is suspected, appropriate laboratory tests (including levels of pancreatic amylase [p-amylase] and lipase) should be obtained via the local laboratory. Imaging studies, such as abdominal CT scan with or without contrast, MRI, or gallbladder ultrasound, should be performed. If laboratory values and/or abdominal imaging support the diagnosis of acute pancreatitis, the patient must discontinue therapy with investigational product, but will continue in the study on another glucose-lowering regimen (details on rescue intervention will be provided). The most appropriate diabetes therapeutic regimen will be decided by the investigator, based on the patient's clinical status. A review of the patient's concomitant medications should be conducted to assess any potential causal relationship with pancreatitis.

Each case of an AE of pancreatitis must be reported. If typical signs and/or symptoms of pancreatitis are present and confirmed by laboratory values (lipase or amylase [total and/or pancreatic]) and imaging studies, the event must be reported as an SAE. For a potential case that does not meet all of these criteria, it is up to the investigator to determine the seriousness of the case (AE or SAE) and the relatedness of the event to study drug.

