##### **9.4.4.4.1. Hyperglycemia and Hypoglycemia Reporting**

Episodes of hyperglycemia (fasting plasma/serum glucose  $>270$  mg/dL [15 mmol/L]) or hypoglycemia (plasma/serum glucose  $\leq 70$  mg/dL [3.9 mmol/L]) will be reported by the investigator or designated physician who will be responsible for advising the patient on what further actions to take. At their discretion, the investigator may request additional monitoring.

If the fasting plasma/serum glucose during the dosing period exceeds the acceptable level, defined as hyperglycemia on 3 or more separate days during any 2-week period between screening and the end of the dosing period, the patient will be evaluated further at the study site.

If fasting plasma/serum glucose continues to exceed the acceptable level, the investigator will discontinue the IP and initiate treatment with an appropriate antidiabetic agent. The patient will continue to be followed up in the study (for safety, PK, and immunogenicity assessment) for at least 28 days after their last dose. If hyperglycemia occurs during the follow-up period, the patient will remain in the study until completion of the planned follow-up.

Site personnel will record hypoglycemia episodes on specific eCRF pages. The investigator will treat hypoglycemia appropriately and may perform additional monitoring of plasma/serum glucose levels. The following categories of the 2017 American Diabetes Association position statement on glycemic targets (American Diabetes Association 2017) on the basis of recommendations of the International Hypoglycaemia Study Group (International Hypoglycaemia Study Group 2017) should be applied for reporting in the eCRF and evaluation of hypoglycemic events.

The main categories of hypoglycemia are outlined as follows:

**Documented Glucose Alert Level (Level 1):** plasma/serum glucose  $\leq 70$  mg/dL (3.9 mmol/L)

- **Documented symptomatic hypoglycemia:** with typical symptoms of hypoglycemia.
- **Documented asymptomatic hypoglycemia:** without typical symptoms of hypoglycemia.
- **Documented unspecified hypoglycemia:** with no information about symptoms of hypoglycemia available. (This has been called unclassifiable hypoglycemia.)

**Documented Clinically Significant Hypoglycemia (Level 2):** with similar criterion as above except for the threshold plasma/serum glucose  $< 54$  mg/dL (3.0 mmol/L)

- **Level 2 documented symptomatic hypoglycemia**
- **Level 2 documented asymptomatic hypoglycemia**

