### 10.2. Populations for Analyses

#### 10.2.1. Study Participant Disposition

All patients who discontinue from the study will be identified and the extent of their participation in the study will be reported. If known, a reason for their discontinuation will be given.

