## 8. DEFINITION OF ANALYSIS POPULATIONS

Safety analyses will be conducted for all enrolled patients, whether or not they completed all protocol requirements.

The Pharmacokinetic population will consist of all patients who received at least 1 dose of the IP and have evaluable PK data.

The Pharmacodynamic population will consist of all patients who received at least 1 dose of the IP and have evaluable PD data.

The Efficacy population will consist of all patients who received at least 1 dose of the IP and have evaluable efficacy data.

All protocol deviations that occur during the study will be considered for their severity/impact and will be taken into consideration when subjects are assigned to analysis populations.

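### Section 8.2 withdraws from the study a patient who needs another glucose-lowering agent, while 9.4.4.2 and 9.4.4.4.1 keep that patient in; separately, the calcitonin stopping rule has no scheduled value to act on while dosing continues

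*Protocol*

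**What the plan says.** **Rescue therapy.** Protocol 8.2 lists circumstances in which patients will be discontinued from the study. One is a need, for any reason, for another agent shown to be effective in the study indication; in that case "discontinuation from the study occurs prior to introduction of the new agent". Two later sections direct otherwise:

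- Protocol 9.4.4.2, when laboratory values or imaging support acute pancreatitis: "the patient must discontinue therapy with investigational product, but will continue in the study on another glucose-lowering regimen".
- Protocol 9.4.4.4.1, when fasting glucose stays above the acceptable level: "the investigator will discontinue the IP and initiate treatment with an appropriate antidiabetic agent". It adds: "The patient will continue to be followed up in the study", for safety, PK and immunogenicity, for at least 28 days after the last dose.

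For visits, Protocol 8 says: "Patients discontinuing from the treatment prematurely for any reason should complete AE and other follow-up procedures per Section 2 of this protocol". Footnote a to the Schedule of Activities asks for ED1 as soon as possible, and then: "The patient will be asked to complete ED2 procedures after a washout period of at least 28 days from the last IP administration".

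**Calcitonin.** Protocol 9.4.4.6 says to stop tirzepatide on a confirmed post-randomization calcitonin of at least 35 ng/L that has risen at least 50% over baseline. It allows a restart in one situation, where another drug that raises calcitonin was in use. The Schedule of Activities has calcitonin at screening, Day 1 predose, Day 113 (Cohort 1) or Day 169 (Cohort 2), and ED1.

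**The concern.** On rescue, the same event leads to opposite instructions. Both are mandatory. The 8.2 item sits under investigator decision, but its wording leaves no discretion and makes no exception. The event is foreseeable: oral agents are stopped in the lead-in (5.1), entry HbA1c may be as high as 10.0% on medication or 10.5% on diet and exercise (6.1), placebo runs for 16 or 24 weeks, and 3.3 names hyperglycemia from washout as a risk.

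Study status then depends on which section the site read. That matters for disposition, since Protocol 10.2.1 states: "All patients who discontinue from the study will be identified and the extent of their participation in the study will be reported". It also matters for adverse events. Under 9.2.1 the investigator need not actively seek them once a patient has discontinued from the study, a point tied there to completion of the summary eCRF.

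On calcitonin, 9.4.4.6 gives a rule for stopping treatment, but the schedule supplies no value while there is still treatment to stop.

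**Working it through.** **Part 1: the instructions side by side.** Take a patient whose persistent hyperglycemia needs another agent.

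- Under 8.2: withdrawn from the study, then the new agent; a study discontinuation under 10.2.1.
- Under 9.4.4.4.1: IP stopped, new agent started, patient still in the study; not a study discontinuation at that point.
- Under 9.4.4.2 (pancreatitis): as 9.4.4.4.1, but with no stated duration.

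Neither 9.4.4.2 nor 9.4.4.4.1 names the visits that a retained patient attends. Only the general sentence in Section 8 points to Section 2, where the columns for early stopping are ED1 and ED2.

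Effect on data:

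- Minimum time to the last contact after IP: 28 days under ED2 and 28 days under 9.4.4.4.1. Difference 28 − 28 = 0 days.
- Content of ED2 in the schedule: AEs, hypoglycemic events, safety laboratory tests, pancreatic enzymes, PK and immunogenicity. These are the domains that 9.4.4.4.1 asks for.

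Weight of one patient, from the planned allocation of 10 tirzepatide to 2 placebo per cohort: 1/10 = 10% of a tirzepatide arm. Pooled placebo is 2 + 2 = 4, so 1/4 = 25%. These are denominators, not expected effects.

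**Part 2: the plan's calcitonin count.** Screening + Day 1 + end-of-treatment visit = 3 samples; 3 × 2.5 mL = 7.5 mL. This reproduces the calcitonin line in Appendix 5 for both cohorts, so no scheduled on-treatment sample has been overlooked.

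Timing, with weekly doses and last doses on Day 106 and Day 162 (Synopsis):

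- Cohort 1: doses = (106 − 1)/7 + 1 = 16. First scheduled post-randomization value is Day 113, and 113 − 106 = 7 days after the last dose.
- Cohort 2: doses = (162 − 1)/7 + 1 = 24. First scheduled value is Day 169, and 169 − 162 = 7 days after the last dose.

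Scheduled values available during dosing are therefore 0 in both cohorts. ED1 can fall earlier, but only in patients who have already discontinued.

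**What an added sample could influence.** The documents give no turnaround time. I assume 7 to 28 days for result plus confirmation. Doses that could still be withheld = (last dose day − first actionable day)/7 + 1.

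- Day 57 sample, actionable Day 64 to Day 85: 7 down to 4 of 16 in Cohort 1; 15 down to 12 of 24 in Cohort 2.
- Day 85 sample, actionable Day 92 to Day 113: 3 down to 0 of 16; 11 down to 8 of 24.

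A Day 57 predose value follows the 2.5 mg and 5 mg doses only. A Day 85 predose value also follows 7.5 mg, but in Cohort 1 it may come too late to act on.

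**Blood volume.** The Appendix 5 lines sum to 368.5 mL (Cohort 1) and 405.5 mL (Cohort 2), shown there rounded as 369 and 406. Adding 2.5 mL gives 371.0 mL (2.5/368.5 = 0.7%) and 408.0 mL (2.5/405.5 = 0.6%).

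**The case against.** On rescue, the best defense is that 9.4.4.2 and 9.4.4.4.1 are specific and 8.2 is general, so a sensible site lets the specific rule govern. Section 9.4.4.2 also promises further details on rescue, and 7.7 leaves continuation of a patient who needs other medication to the investigator after sponsor consultation. SAP 9.2 only lists disposition, and with about 24 patients a rescue case will be visible whatever its label. Most of this stands and keeps the point minor. It does not remove the conflict: 8.2 speaks directly to antidiabetic agents, excludes no reason, and is nowhere subordinated to the other sections.

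A reader might infer that rescued patients are lost to follow-up or drop out of the primary safety analysis. The documents do not support that. ED1 and ED2 apply, and SAP 8 says: "Safety analyses will be conducted for all enrolled patients, whether or not they completed all protocol requirements". A reader might also infer that events after rescue contaminate the treatment-emergent counts undetectably, because the definition in SAP 9.6.1 has no end date. But all AEs are listed, AEs are presented by week of onset, concomitant medication is listed, and no inferential safety analysis is planned. Such events can be identified.

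On calcitonin, 9.4.4.6 gives the purpose of measurement as assessing C-cell function, which a start-and-end pair can describe. The rule covers any post-randomization value, and its confirmation and post-washout tests are necessarily unscheduled. This stands, and it is why the point is an improvement and not an error. It would go too far to call the rule inoperable or the thyroid unmonitored: unscheduled tests are allowed. Nor do the documents plainly make a dose withheld under 9.4.4.6 a missed dose under the noncompliance rule in 7.6.

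**Conclusion.** Part 1 is wrong as written, and minor. Sections 8.2, 9.4.4.2 and 9.4.4.4.1 cannot all be followed for the same patient. The effect is on study status, disposition and how long AEs are actively sought. The difference in minimum follow-up is 0 days against 9.4.4.4.1. How far active AE seeking would be cut short depends on when the summary eCRF is completed, which the documents do not say. They also give no expected number of rescued patients, so no effect on any estimate can be quantified.

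Part 2 is a cheap improvement. Across 16 or 24 doses there is no scheduled post-randomization calcitonin value, and the first comes 7 days after the last dose in both cohorts. That rests on the schedule and Appendix 5 alone. The counts of doses that could still be withheld rest on the assumed 7 to 28 days.

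The study is descriptive, so neither part touches a power or error-rate figure.

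**What to change.** **Section 8.2.** Keep the bullet, so that it still covers every other reason for needing a new agent, and add: *except as provided in 9.4.4.2 and 9.4.4.4.1, where IP is stopped, the new agent may start, and the patient stays in the study and completes ED1 as soon as possible and ED2 at least 28 days after the last dose.* This also names the visits for a retained patient. It costs one clause.

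**Calcitonin.** Add one predose sample at an existing on-treatment draw in both cohorts, for example Day 57 (Visit 7), and change the Appendix 5 calcitonin line from 3 to 4 samples (7.5 to 10 mL). The cost is 2.5 mL and one assay per patient, with no new visit or needle stick, and possibly some confirmatory repeats. Keep the end-of-treatment sample. Doses from Day 57 onward (8 of 16 in Cohort 1, 16 of 24 in Cohort 2), which include everything from 7.5 mg up, would still have no scheduled check before dosing ends.
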